#### **8.1.2.2.2.2 Sensitivity Analysis 2.2: Control-based MI**

The control-based imputation method used the data from the subjects randomized in the placebo group to impute the missing value for the subjects in the PSL treatment groups. This assumes the subjects on PSL treatment groups will have their efficacy trend toward that of the subjects in the placebo group after the treatment discontinuation. Missing data for the first visit interval are imputed, then missing data for the second visit interval are imputed using observed data and missing data just imputed for the first interval; and so on to the final interval. The imputation will be performed via the sequential regression method using PROC MI statement MONOTONE REG. Multiple imputed datasets will be analyzed using the same ANCOVA model as in the primary analysis. If there are issues with model convergence, covariates will be dropped sequentially in the order of Region, and then Baseline SV2A use (Yes or No) if further needed. Seed=14823.

#### **8.1.2.2.2.3 Sensitivity Analysis 2.3 Tipping point MI**

Following the National Research Council (NRC) report on missing data (NRC, 2010), a sensitivity analysis using tipping point method to stress-test the result of MAR by imposing a succession of  $\delta$  adjustments, each one more severe, in the PSL Groups until they are no longer statistically significant. This Delta ( $\delta$ ) will be applied just once, at the first visit that has missing frequency seizure data for each subject in the PSL groups who discontinued before the end of treatment period and hence have missing records for "seizure frequencies". Use nimpute = 30, seed = 56432.

The tipping point report (table) for each pairwise comparison will include values for the LSmeans, the 95% CI, and the p-value for each of the delta value (including 0, until p-values are

no longer statistically significant. Only 8 delta values will be tabulated in the report including  $\delta=0$  until  $\delta=xx.x\%$  shift the p-value to larger than multiplicity adjusted alpha level.

### **8.1.2.3 Primary variable for submission to the EMA and regulatory authorities who reference EMA**

The primary efficacy available for the EMA is the 75% responder rate over the 12-week Maintenance Period. Analyses of the primary variable for the EMA submission will be done on the FAS as described below.

The analysis of 75% responder rate will be based on a logistic regression model with factors for treatment group (PSL 400mg bid, 200mg bid, 100mg bid, 50mg bid and placebo), Region (Europe or Non-Europe), Baseline SV2A use (Yes or No) and log-transformed Baseline seizure frequency as a continuous covariate. If there are issues with convergence, covariates will be dropped sequentially in the order of Region, and then Baseline SV2A use (Yes or No) if further needed. Odds Ratios of PSL dose to placebo will be obtained and tested for difference from unity (2-sided) for the dose groups 400mg bid, 200mg bid, and 100mg bid. The evaluation of statistical significance will be based on the Hochberg procedure as described in Section 4.5. If all 3 Odds Ratios of PSL dose relative to placebo are statistically significant, then the 50mg bid dose group will be compared to placebo by testing the Odds Ratio for difference from unity, too. Both multiplicity adjusted p-values and unadjusted p-value will be presented.

If there is <2 responders in a treatment group, results will also be provided for an exact conditional logistic regression model where treatment group is included in the model and Region (Europe or Non-Europe) and Baseline SV2A use (Yes or No) are included as strata.

### **8.1.2.4 Supportive and sensitivity analyses for the primary variable for submission to the EMA and regulatory authorities who reference EMA**

#### **8.1.2.4.1 Sensitivity analysis 1: PPS**

The primary analysis (75% responder rate) for submission to the European regulatory agency as described in Section 8.1.2.3 will be repeated using the PPS.

#### **8.1.2.4.2 Sensitivity analysis 2: non-responder imputation**

A sensitivity analysis of the 75% responder rate will be performed in which subjects who discontinued prior to the end of the Maintenance Period will be treated as non-responders. The primary analysis in Section 8.1.2.3 will be repeated.

#### **8.1.2.4.3 Sensitivity analysis 3: multiple imputation**

After the multiple imputation process described in Section 8.1.2.2.2, seizure frequency during the Maintenance Period will be calculated as  $[\exp(\log\text{-transformed seizure frequency}) - 1]$  and the 75% responder status will be derived. Multiple imputed datasets will be analyzed using the same logistic regression model as in the primary analysis for the MAR imputation and control-based imputation respectively. If there are issues with model convergence, covariates will be dropped sequentially in the order of Region, and then Baseline SV2A use (Yes or No) if further needed. The tipping point analysis based on MAR multiple imputation will be repeated until

none of the PSL treatment group is significantly different from placebo based on the logistic regression model.

### **8.1.2.5 The log of the odds ratio estimates from the logistic regression model are used when combining into a single inference using SAS PROC MIANALYZE. Subgroup analyses for the primary variables**

The analyses described in Section 8.1.2.1 and 8.1.2.3 will be repeated for the subgroups described in Section 4.8. In the subgroup analyses by region and Baseline SV2A use, the corresponding stratification factor will be removed from the model. These evaluations will be descriptive, and the model estimates and 95% CIs will be presented.

## **8.2 Statistical analysis of the secondary efficacy variables**

Separate secondary efficacy variables have been designated for submission to US FDA/PMDA and submission to EMA.

### **8.2.1 Analysis of the secondary efficacy variables for submission to the US FDA, PMDA, and other regulatory authorities not referencing EMA**

#### **8.2.1.1 75% Responder Rate over the 12-week Maintenance Period**

75% responder rate is the secondary efficacy variable for the US FDA and primary efficacy variable for the EMA. The analyses are described in Section 8.1.2.3.

#### **8.2.1.2 50% Responder Rate over the 12-week Maintenance Period**

Subjects with at least a 50% reduction in seizure frequency will be categorized as a 50% responder. The same methodology described in Section 8.1.2.3 will be used for 50% responder rate during the 12-week Maintenance Period. No multiplicity adjustment will be applied and tests will be carried out at a nominal two-sided 0.05 significance level.

#### **8.2.1.3 Percent reduction from Baseline in observable focal-onset seizure frequency over the 12-week Maintenance Period**

The third secondary efficacy variable is percent reduction from Baseline in observable focal-onset seizure frequency, over the 12-week Maintenance Period. The calculation of percent reduction from Baseline in seizure frequency is described in Section 8.1.1.2. The percent reduction in seizure frequency will be summarized descriptively.

Statistical comparisons between each PSL dose group and placebo will be performed on the FAS using the Wilcoxon-Mann-Whitney test. No multiplicity adjustment will be applied and tests will be carried out at a nominal two-sided 0.05 significance level. The Hodges-Lehmann nonparametric estimator will be used to estimate the median difference between each PSL dose group versus placebo, along with the corresponding 95% CI of the estimate.

In addition, the number and percentage of subjects within each of the following categories of percent reduction from Baseline will be summarized: <-25%, -25% to <25%, 25% to <50%, 50% to <75%, 75% to <100%, and 100%.

## **8.2.2 Analysis of the secondary efficacy variables for submission to EMA and regulatory authorities who reference EMA**

### **8.2.2.1 The change in log-transformed observable focal onset seizure frequency from Baseline, over the 12-week Maintenance Period**

The analysis described in Section 8.1.2.2 (for US FDA, PMDA, and other regulatory authorities not referencing EMA) of the change in log-transformed observable focal-onset seizure frequency from Baseline, over the 12-week Maintenance Period, serves as the key secondary variable for submission to EMA.

### **8.2.2.2 50% Responder Rate status over the 12-week Maintenance Period**

This variable is also a secondary variable for FDA submission and is described in Section 8.2.1.2.

### **8.2.2.3 Percent reduction in observable focal-onset seizure frequency from Baseline, over the 12-week Maintenance Period**

This variable is also a secondary variable for FDA submission and is described in Section 8.2.1.3.

## **8.3 Analysis of other efficacy variables**

Other efficacy variables are listed in Section 2.2.1.3. These variables are the same for all regulatory agencies.

### **8.3.1 Derivations of other efficacy variables**

For other efficacy variables based on seizure frequencies (observable focal-onset (Types IA1, IB, IC) and all Type I focal-onset seizures the frequencies), log-transformations, changes from Baseline, percent reduction from Baseline and Responder Rates during the evaluation period of interest are calculated similarly as described in Section 8.1.1, using the appropriate analysis period and responder criterion.

#### **8.3.1.1 Seizure-freedom status (Yes/No)**

A subject is defined as seizure free (ie, seizure-freedom status=Yes) during a specific evaluation period if they meet all of the following criteria:

1. The subject completed the specific time period.
2. The subject did not have any missing diary days over the time period. Missing diary day refers to no diary available at all for that day. If the diary for the day is present and 'no seizures' is checked then the diary day is not missing.
3. The subject did not report any seizure of any type over the time period.

#### **8.3.1.2 Seizure-free days**

The number of seizure-free days will be the total number of days within an interval for which daily diary data was available and indicated that no seizures occurred. The percentage of seizure-free days will be computed as 100 times the number of seizure-free days divided by the number of days for which daily diary data was available. Days without the corresponding daily diary data will not be used in these computations.

### **8.3.1.3 Seizure Severity Global Item (SSG) variables**

The SSG consists of 1 item at baseline or 2 items during follow up from the Seizure Severity Questionnaire and asks the subjects to evaluate the severity of their seizures for the last 4 weeks and/or since the Baseline. The subject describes all seizure types when answering the questions.

The SSG is completed according to the schedule of study procedures in Table 2-2 (Visits 2, 4, 7 and 9) and is provided to each subject at the beginning of the visit. The SSG data are collected on 2 separate CRFs. On the “Seizure Severity Global Item – Baseline”, seizure-intensity during the last 4 weeks is collected on a 7-point scale with 7 = very severe; On the “Seizure Severity Global Item – Follow-up” CRF, seizure-intensity during last 4 weeks is collected on a 7-point scale with 7 as very severe. Assessment of change since starting IMP, is also collected on a 7-point scale with 7 = much worse.

### **8.3.1.4 QOLIE-31-P variables**

The QOLIE-31-P assesses subject functioning and health-related quality of life. The QOLIE-31-P (Cramer et al, 2003) is an adaptation of the original QOLIE-31 instrument (Cramer et al, 1998) that includes 31 items grouped into 7 multi item subscales (Seizure Worry [5 items], Overall Quality of Life [2 items], Emotional Well-being [5 items], Energy/Fatigue [4 items], Cognitive Functioning [6 items], Medication Effects [3 items], and Daily Activities/Social Functioning [5 items]) and 1 health status item.

In addition to the 31 items of the QOLIE-31, the QOLIE-31-P contains 7 items assessing the degree of “distress” associated with the topic of each subscale (ie, distress items) and 1 item asking about the relative importance of each subscale topic (ie, prioritization item).

The QOLIE-31-P will be completed according to the schedule of study procedures in Table 2-2 (Visits 2, 4, 7 and 9) and is provided to each subject at the beginning of the visit. The subject completes the questionnaire on his/her own. The Investigator or designee will verify that all questions have been answered. Further details about the QOLIE-31-P are provided in the scoring manual.

### **8.3.1.5 Hospital Anxiety and Depression Scale (HADS) score variables**

The HADS is administered at Visits 2, 4, 7 and 9. The HADS scores for anxiety and for depression range from 0-21 with higher scores indicating a worse state. A score below 8 is considered to be normal (Zigmond and Snaith, 1983). HADS subscale scores will be determined by summing the scores of the 7 items belonging to each of the two subscales, i.e. anxiety (odd numbered questions) and depression (even numbered questions). The following rules will be applied for the computation of the subscale scores: 1) Missing items values will be set to the mean score of the subscale to which the item belongs, provided 50% or more of the items within the subscale are present. 2) The subscale scores will be calculated if 50% or more of the items within a subscale are present.

### **8.3.2 Analysis of other efficacy variables**

Other efficacy variables and tests will be carried out at a nominal two-sided 0.05 significance level and no multiplicity adjustments will be applied.

### **8.3.2.1 Change from Baseline in log-transformed observable focal-onset seizure frequency over the first 4 weeks, second 4 weeks, and third 4 weeks of the 12-week Maintenance Period**

The 28-day adjusted seizure frequencies during the Treatment Period will be computed using observed diary records for the following 4-week intervals: Visit 2 to Visit 4, Visit 4 to Visit 5, Visit 5 to Visit 6, and Visit 6 to Visit 7. The 28-day adjusted seizure frequency during the Treatment Period and change from baseline based on the observed data will be summarized descriptively by the 4-week interval.

The change from Baseline in log-transformed observable focal-onset seizure frequency by 4-week interval will be analyzed using a Mixed Model Repeated Measures (MMRM) model, including Baseline log-transformed seizure frequency as a continuous fixed effect covariate, and treatment, Region (Europe or Non-Europe), Baseline SV2A use (Yes or No), and visit as fixed effect factors, and Baseline  $\times$  visit and treatment  $\times$  visit interactions. MMRM assumes that missing data are missing at random and estimates the mean outcome at each time interval by treatment group. An unstructured covariance structure will be used. If the model does not converge, an appropriate covariance structure will be used instead. Estimates of effects and comparison contrasts and CI will be back-transformed for display in tables as described in Section 8.1.2.1.

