UCB regards the 12-week duration for the Maintenance Period as adequate to distinguish long-term from short-term efficacy. Moreover, 12 weeks is consistent with registration studies for recently approved AEDs as adjunctive therapy for focal-onset seizures (Moseley et al, 2016; Chung et al, 2010b; Elger et al, 2009) and conforms to the guidance documents by the FDA, Guidance for Industry, 1981 and European Medicines Agency (CHMP/EWP/566/98 Rev.2/Corr, 2010). Given the increased risk of SUDEP in patients with uncontrolled seizures (Jehi, 2016) and in those randomized to placebo in clinical trials (Ryvlin et al, 2011), UCB considers that requiring patients to remain on placebo longer or for all enrolled patients to exclude dose adjustments is not acceptable. Because of the increased incidence of SUDEP, subjects should be monitored closely and, depending on the Investigator's judgment, withdrawn from the study in the event of seizure worsening, particularly subjects experiencing an increase in secondarily generalized seizures. Additionally, a 3-week Titration Period, a 1-week Stabilization Period, and a 12-week Maintenance Period has been assessed as adequate to evaluate the potential for the development of tolerance to BZDs associated with a reduction in long-term efficacy for both clobazam and brivaracetam.

Similarly, UCB proposes to perform an examination of the reduction in seizure frequency from Baseline to assess whether there is any evidence of a notable change in treatment effect during the course of the 16-week Treatment Period for EP0091, and subsequent registration studies.

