**Figure 2–1: Study design**

## 2.7 Determination of sample size

The sample size was calculated based on achieving 90% power to observe a statistically significant result for either the 400mg bid and 200mg bid or 200mg bid and 100mg bid doses when compared to placebo, for a change from Baseline of the log-transformed ( $\ln x + 1$ ) 28-day adjusted seizure frequency. Multiplicity is controlled for using the Hochberg step up procedure.

The log-reduction from Baseline in seizure frequency was assumed to be 0.195 for placebo and 0.492, 0.670, 0.754, and 0.780 for the 50mg bid, 100mg bid, 200mg bid, and 400mg bid doses of PSL, respectively. A common SD of 0.985 was assumed. These estimates are based on prior experience in epilepsy together with the EP0069 study results.

With power of 90%, a 2-sided Type-1 error of 5%, and all dose groups of the same size, 80 subjects are required per arm, giving a total of 400 subjects.

Assuming a screening failure rate of approximately 20%, it is anticipated to enroll around 500 subjects and randomize 400 subjects in this study.

The study is also powered to give over 80% power to observe a statistically significant result for the 75% response rate. For the 75% responder rate, assumptions were a 0.121 responder rate for placebo and corresponding responder rates of 0.233, 0.301, 0.332, and 0.342 for the 50mg bid, 100mg bid, 200mg bid, and 400mg bid doses of PSL, respectively.

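### The SAP's by-interval model gives PSL-versus-placebo effects within each 4-week interval but no estimate or confidence interval for the change in effect over time, which is what the protocol asks about

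*SAP*

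**What the plan says.** Protocol 5.4.1 describes the titration, stabilization and maintenance schedule as adequate to evaluate tolerance of the benzodiazepine kind. It then proposes an examination of the reduction in seizure frequency "to assess whether there is any evidence of a notable change in treatment effect during the course of the 16-week Treatment Period".

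SAP 8.3.2.1 is where seizure frequency is modelled by time. Four intervals are defined: Visit 2 to 4 (titration and stabilization), then Visit 4 to 5, 5 to 6 and 6 to 7. Beside a descriptive summary there is one MMRM on the log change from Baseline, with treatment-by-visit and baseline-by-visit interactions and an unstructured covariance. The model "estimates the mean outcome at each time interval by treatment group". Effects, comparison contrasts and CIs are to be back-transformed as in SAP 8.1.2.1, and that section defines only the log ratio of each PSL group to placebo. Under SAP 8.3.2, tests of the other efficacy variables "will be carried out at a nominal two-sided 0.05 significance level and no multiplicity adjustments will be applied".

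No contrast between intervals is named, no test of the treatment-by-visit term is specified, and notable is not defined.

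**The concern.** Tolerance asks about a difference of differences: is the PSL-placebo difference late in Maintenance smaller than it was early in Maintenance? The specified output gives the two differences separately. Whether one is significant and the other is not says little about their difference, because the same subjects contribute to both and the correlation between intervals enters only when the two are contrasted directly. Two overlapping CIs have the same weakness.

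At stake is what the report can say about loss of efficacy, which the protocol raises for a drug acting partly at the benzodiazepine site. Without the contrast, any statement in either direction has to be built from a pattern of interval results that does not measure the change.

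**Working it through.** **1. Inputs.** SAP 2.7 gives 80 per arm and SD 0.985. The placebo log-reduction "was assumed to be 0.195 for placebo", against 0.670, 0.754 and 0.780 for 100, 200 and 400mg bid. The placebo-corrected effects are therefore 0.670 − 0.195 = 0.475, 0.754 − 0.195 = 0.559 and 0.780 − 0.195 = 0.585. Half the 400mg bid effect is 0.2925.

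**2. The plan's own figure.** "With power of 90%, a 2-sided Type-1 error of 5%, and all dose groups of the same size, 80 subjects are required per arm", with success defined "for either the 400mg bid and 200mg bid or 200mg bid and 100mg bid doses when compared to placebo" under Hochberg. Simulating three dose-placebo statistics that share one placebo arm gives 90.5% for 400 and 200mg bid both significant, and 91.5% for either named pair. The stated 90% is reproduced, so these inputs are a sound base.

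**3. Assumptions the documents do not supply.** These are a common correlation ρ between intervals, the SD σ of a single interval, and dropout. I take ρ = 0.5, 0.7 and 0.8 and no dropout. I choose σ so that the mean of three intervals has SD 0.985, which treats the 12-week log change as approximately that mean:

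σ = 0.985 × √(3 / (1 + 2ρ))

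**4. Precision of the change in effect, one dose against placebo.**

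SE = σ × √(2(1 − ρ)) × √(2/80), half-width = 1.96 × SE

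| ρ | σ | SE | 95% half-width |
|---|---|---|---|
| 0.5 | 1.206 | 1.206 × 1.000 × 0.1581 = 0.191 | 0.37 |
| 0.7 | 1.101 | 1.101 × 0.775 × 0.1581 = 0.135 | 0.26 |
| 0.8 | 1.058 | 1.058 × 0.632 × 0.1581 = 0.106 | 0.21 |

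A CI centred on no change would not exclude a halving (0.29) at ρ = 0.5. It would at 0.7 and 0.8.

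**5. Three higher doses averaged.** Replace √(2/80) by √(1/80 + 1/240) = 0.1291, a factor of 0.1291 / 0.1581 = 0.816. The half-widths become about 0.31, 0.22 and 0.17. The average effect is (0.475 + 0.559 + 0.585) / 3 = 0.540, and half of it is 0.27.

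**6. Sensitivity.** If σ is simply 0.985 in each interval, the single-dose half-widths are 0.305, 0.236 and 0.193. With 64 per arm (20% loss) and σ 20% above 0.985 they are 0.41, 0.32 and 0.26.

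**7. Why the pattern of significance is not a substitute.** With the inputs of step 3 and a truly constant effect, the three Maintenance intervals are not all significant in 11% to 28% of trials at 400mg bid and in 30% to 53% at 100mg bid. If the 400mg bid effect has halved by the third interval, that interval is still significant 33% to 42% of the time. The pattern can suggest waning where there is none and conceal it where there is.

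**The case against.** The strongest reply is that this is one repeated-measures model with a treatment-by-visit term and an unstructured covariance, so the wanted quantity is already in the fit and could be extracted at any time. That is correct, and it would be wrong to describe the plan as separate tests per interval. But the contrast is not specified, and one chosen after unblinding carries less weight. The other time-related analyses do not fill the gap. The Kaplan-Meier time to the Baseline count (SAP 8.3.2.22) accumulates from the start of Maintenance, and SAP 8.3.2.23 is descriptive by period.

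A reader might infer that the sponsor will declare the effect maintained whenever nothing is significant. Neither document says so. Protocol 5.4.1 proposes an examination and gives no rule.

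A reader might also infer that the plan would miss a halving of effect about half the time. That figure is not supported as a general statement. For a direct test of the change at 400mg bid, the miss rate runs from 67% at ρ = 0.5 to 2% at ρ = 0.9 with the σ of step 3, and from 74% at ρ = 0 to 1% at ρ = 0.9 with σ = 0.985. It also describes the recommended contrast, not the planned output.

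Finally, tolerance appears in the design rationale and not among the objectives, and the variable sits in the lowest efficacy tier. That stands, and it argues against a formal margin rule. A margin of half the observed first-interval effect would also be data-dependent.

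**Conclusion.** The gap is real and limited. The protocol asks about a change in treatment effect, and the SAP specifies effects within intervals but no estimate or CI of the change. The documents do not support a stronger conclusion, either that non-significance will be taken as proof of maintenance or that a halving would be missed at any fixed rate.

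The half-widths of about 0.37, 0.26 and 0.21 rest on 80 per arm, no dropout, a common correlation and the derived interval SD. Dropout or a larger interval SD would widen them. No primary or secondary conclusion depends on this point.

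**What to change.** In SAP 8.3.2.1, pre-specify from the same MMRM the contrast [PSL minus placebo, Visit 6 to 7] minus [PSL minus placebo, Visit 4 to 5], for each dose and averaged over the three higher doses, with a back-transformed estimate and 95% CI. Start from Visit 4 to 5 because the preceding interval is titration and stabilization. Add a sentence that any statement about maintained or waning effect rests on this estimate and CI, not on which intervals reach significance.

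The cost is one or two estimate statements, a few table rows and a sentence. No new data are needed and the primary analysis is untouched. The downside is that single-dose CIs may be wide, so the honest result may be inconclusive. The contrast supplies the missing estimate; it does not raise power.
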